 - clinically significant apnoea *and/or*
 - clinically significant desaturation *and/or*
 - clinically significant bradycardia
- Apnoea
 - clinically significant apnoea was defined as a pause in breathing, as measured by the Philips cotside monitor, which:
 - lasts more than 15s in duration, *or*
 - was accompanied by clinically significant desaturation and/or bradycardia as defined below, *or*
 - required intervention (manual stimulation, PEEP or IPPV)
- Bradycardia
 - clinically significant bradycardia was defined as heart rate < 100 for $\geq 5s$ as measured by Philips cotside monitor with a 5s averaging time
- Desaturation
 - clinically significant oxygen desaturation was defined as $SpO_2 < 80\%$ for $\geq 5s$ as measured by Philips cotside monitor with a 5s averaging time

Primary Outcomes

This study will measure the number of respiratory events and oximetry histograms during each of the 24h condition periods:

- Number of respiratory events:
 - Defined as total number of clinically significant:
 - Apnoeic events
 - Desaturations
 - Bradycardic events
- Percentage of time spent with $SpO_2 < 80\%$ over the 24h testing period

Secondary Outcomes

- Percentage of time spent with $SpO_2 \geq 88\%$ over the 24h testing period

Effect Size

A clinically significant effect was defined for each of the three outcomes:

- 40% reduction in number of respiratory events
- 50% improvement in percentage of time spent with $SpO_2 \geq 88\%$ over the 24h testing period
- 50% reduction in percentage of time spent with $SpO_2 < 80\%$ over the 24h testing period

Data Collection

The following demographic and clinical data will be recorded for each infant on enrolment in order to describe our sample:

- Gender
- Gestational age at birth
- Chronological age and Corrected gestational age
- Birth weight
- Current weight
- Feed volumes (mL/kg/day)
- Caffeine administration

All infants enrolled in the study will be monitored using the same standard cardiorespiratory monitoring and nursing observations employed for all babies managed in the unit. The following clinical data will be recorded in order to test the primary hypothesis:

- Number of respiratory events

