 - Apnoeas, desaturation and bradycardic events, as defined previously, will be counted and totalled for each 24 hour period by retrospective review of the central monitor. This data will also be reconciled with a nursing observation sheet in order to identify issues with lead contact, cares or events requiring intervention.
- Oximetry histogram
 - The percentage of time spent with oxygen saturations $\geq 88\%$ and $<80\%$ will be recorded using the histogram feature of the Philips monitors at the cot-side at the conclusion of each 24 hour condition period

Blinding

Data collection for number of respiratory events will be blinded, as it relies on examining the monitoring trace for each 24 hour condition period and counting the number of events. While the trace will identify which baby is being monitored, the researcher counting the events will be blind to the test condition for each 24 hour period. The histogram data is completely objective, derived from the monitors, and can be printed at the end of each 24h condition period.

Study Design

Design

This study will employ a randomised triple crossover design. In this approach, each infant will experience each of the three test conditions in a sequence which is randomised. Thus each infant will serve as its own control, and variance within and between infants can be measured. Benefits of a crossover design include smaller sample size requirements compared to equivalent parallel-group trials in order to meet the same criteria in terms of type I and type II error risks³⁹. In addition, each infant is managed equivalently in every respect, excepting the actual order of the test conditions experienced – thus no infant should be advantaged or otherwise relative to the other infants enrolled in the study as each infant is exposed to the same conditions.

In general terms, crossover design is appropriate when:

- The underlying disease is similar during all treatments, i.e. not cured by one of the treatments and not of a short duration relative to the treatment period. It is necessary to separate period effects from treatment effects. This is the case in this study, as we are examining respiratory events which occur as a result of feeding. A feed-related intervention should only have any effect on events during and after the actual feed, and will not be curative of respiratory events in subsequent feeds.

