Nutritional requirements vary with the post-gestational age and condition of any given baby. Most preterm infants will progress temporally from parenteral nutrition (provided through a cannula) to enteral nutrition with a nasogastric tube (feeding tube) to suck feeds (breast or bottle feeding) before being considered suitable for discharge. Nasogastric feeds may be administered continuously by pump (given at a continuous rate measured in mL/hr) or more commonly, bolus (a volume of milk/formula is given at a particular time interval, usually every 2 to 3 hours). Furthermore, bolus feeds may be given by gravity ('as quickly as the tube will accommodate') or pump (a rate can be specified to give the feed over a longer period of time). Most babies begin enteral feeds as bolus feeds with smaller volumes given every 2 hours, and then progress to 3 hourly feeds. Such feeds are usually administered by gravity bolus, however clinical factors may warrant reducing the feed rate (e.g. giving the same bolus volume over 45min).

Infants will undergo test conditions in combinations of feed and position conditions, as outlined in Table 1. Infant and cot positional interventions, where possible, will be maintained throughout the entirety of the 24h condition period, with the exception of routine nursing cares and brief interactions with parents and caregivers.

Table 1: Test Conditions Employed in the FIBRE Study

	Infant Position	Cot Position	Rate of Feed
Condition A Control	Supine	Flat	Bolus gravity feed
Condition B Position intervention	Prone	Propped (15 degrees)	Bolus gravity feed
Condition C Feed rate intervention	Supine	Flat	Continuous pump feed over 45 min

Timecourse

Each condition continues for 24 hours before switching to the next condition. Thus each infant will experience each intervention over a 3 day period of enrolment, with the order of progression through conditions randomly assigned. No washout period will be required between conditions, as respiratory events should be related to the period during and immediately post-feed (i.e. the effect of the previous test condition should have disappeared well before the first feed in the next test condition).

Randomisation

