Infants will be randomly assigned to one of six sequence groups ABC/ACB/BCA/BAC/CAB/CBA, as outlined in Table 2. This will permit assessment of potential period effects and carryover effects, as each treatment follows every other treatment at least once in the six sequence design, as opposed to a simpler Latin Square approach. Randomisation will be achieved through the use of a computer generated sequential list, thus dictating the sequence of conditions.

Table 2: Test Conditions Employed in the FIBRE Study

Group	Sequence Group
1	ABC
2	ACB
3	BAC
4	BCA
5	CAB
6	CBA

Size and Power Considerations

We will use a 5% significance level ($\alpha = 0.05$) for all comparisons. The expected sample was sized using a two-sided test, as there is no strong expectation that effect size would only be in one direction. A small pilot was conducted using $n = 10$ babies using existing monitor data, and measuring three outcomes sequentially over three days for each baby:

- Number of respiratory events (primary outcome)
- Percentage of time spent with SpO₂ < 80% over the 24h testing period (primary outcome)
- Percentage of time spent with SpO₂ \geq 88% over the 24h testing period (secondary outcome)

The observed baseline data was right-skewed, thus a log transformation was applied. The between (σ_s^2) and within subject variance (σ^2) were estimated by fitting a variance components model to the log-transformed baseline audit data for each of the three outcomes.

The sample size formula for a two-sided cross-over study design is shown in Equation 1, where n_c is the minimum total sample size required for cross-over design, and $Z_{\frac{\alpha}{2}}$ and Z_β are the values of the standard normal distribution that cut off probability $\frac{\alpha}{2}$ and β in the upper tail respectively, σ^2 is the within-subject variance and Δ is the minimum difference to be detected. For cross-over studies the variance term depends only on the within-subject variance:

$$n_c = \frac{2 \left(Z_{\frac{\alpha}{2}} + Z_\beta \right)^2 (\sigma^2)}{\Delta^2}$$

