The correlation between two observations from the same subject (ρ) is given by $\rho = \sigma_s^2 / (\sigma_s^2 + \sigma^2)$. The more correlated the observations from the same subject (i.e. the closer ρ is to 1), the smaller the sample size required for a cross-over design compared to an equivalent parallel design. Baseline audit data showed a correlation of approximately 0.6 for the number of events and correlations approximating 0.4 for the histogram outcomes; hence the required crossover sample size is much smaller for all three outcomes of interest to achieve similar power.

A clinically significant effect was defined for each of the three outcomes based on considerations of an effect which might modify practice:

- a 40% reduction in number of respiratory events ($n_c = 87$ infants, $1 - \beta = 0.8$)
- a 50% improvement in percentage of time spent with SpO₂ \geq 88% ($n_c = 79$ infants, $1 - \beta = 0.8$)
- a 50% reduction in percentage of time spent with SpO₂ < 80% ($n_c = 108$ infants, $1 - \beta = 0.8$)

A sample size of 90 infants would produce a study with 80% power to compare both primary outcomes, and 70% power to compare the secondary outcome.

Design Consultation

Consultation has been sought from a senior statistician at Griffith University (Gold Coast, Australia) and through a private Consultant Statistician (Data Analysis Australia Pty Ltd) which has guided design. One of the associate researchers is a consultant neonatologist with experience in education and research, and has been actively involved in the proposal design and offered clinical perspective on design parameters and outcomes. We have also sought and utilised advice from the Clinical Director of the Newborn Care Unit in which the study is taking place, as well as other neonatologists in the unit, particularly in relation to defining clinically significant effect sizes.

Analysis

A mixed effect model will be employed to analyse this crossover study. This approach has the advantages that all three treatment effects for a given outcome can be modelled together, and incomplete records in the case of dropouts can still contribute to the model fit and the method can handle unbalanced data. Standard analysis methods exclude incomplete records and so the study can quickly become underpowered when patients don't complete all treatments.

Consent

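### The event count is a raw total per nominal 24 hours with no record of valid monitored time, so unequal monitoring loss between conditions would pass for a treatment effect

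*Protocol*

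**What the plan says.** Protocol, Primary Outcomes, gives the event outcome as a sum over three event types: "Defined as total number of clinically significant" apnoeas, desaturations and bradycardias. Data Collection says how it is obtained: the events "will be counted and totalled for each 24 hour period by retrospective review of the central monitor". The same item says the data are "reconciled with a nursing observation sheet in order to identify issues with lead contact, cares or events requiring intervention". It does not say what then happens to a flagged stretch of trace or to an event inside it. No list of recorded data includes the hours of usable monitoring.

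The period length is nominal. Timecourse says "Each condition continues for 24 hours before switching to the next condition". The text before Table 1 has the assigned position kept where possible, "with the exception of routine nursing cares and brief interactions with parents and caregivers".

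The other primary outcome (SpO2 below 80%) and the secondary outcome (SpO2 of 88% or more) are percentages of time, so each has a time denominator. The event count has none.

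The Analysis section plans a mixed effect model and names no exposure term. It says "incomplete records in the case of dropouts can still contribute to the model fit" and explains that, under standard methods, "the study can quickly become underpowered when patients don't complete all treatments".

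**The concern.** A count over a fixed window compares conditions fairly only if the usable part of the window is the same in each. The protocol itself expects interruptions from lead contact and cares. Conditions A and C are supine and flat, while B is prone with the cot propped at 15 degrees, so it is plausible, though not documented, that usable time differs between B and the other two.

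Such a difference would travel with the condition. Randomising the sequence would not remove it, and neither would blinding the person who counts the events. Fewer usable hours would mean fewer counted events, and the comparison would read that as benefit. A 24 h period that ends early and is entered as a full total would have the same effect.

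The gap lies in data capture as well as in analysis. If valid hours are not recorded, a later analysis plan has no denominator to use.

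**Working it through.** **Inputs from the protocol** (Size and Power Considerations): two-sided alpha 0.05; power 0.80; a 40% reduction in events, i.e. a ratio of 0.60; n_c = 87; planned N = 90; log-transformed pilot data used for sizing; Equation 1, n_c = 2(z_{α/2} + z_β)²σ²/Δ².

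**Not given:** the within-infant variance σ², and any figure for lost monitoring. The first is back-solved and the second is assumed over a range.

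**Step 1: the plan's own figure.** Because σ² is not stated, n_c = 87 cannot be reproduced independently. Taking Δ = |ln 0.60| = 0.5108 and (1.960 + 0.842)² = 7.849:

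σ² = 87 × 0.5108² / (2 × 7.849) = 1.446.

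At N = 90 the standard error of the log ratio is √(2 × 1.446/90) = 0.179. Power is Φ(0.5108/0.179 − 1.96) = 81.3%, which agrees with the stated 80% for this outcome.

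**Step 2: one-sided loss, no true effect.** Suppose one condition loses a fraction L of valid time that the comparator does not lose, and that events are as frequent in lost as in valid time. The apparent ratio is 1 − L and the bias on the log scale is b = |ln(1 − L)|. The two-sided rejection probability is Φ(b/0.179 − 1.96) + Φ(−b/0.179 − 1.96).

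| Assumed L | Apparent ratio | b as share of 0.5108 | False-positive rate |
|---|---|---|---|
| 0% | 1.00 | 0% | 5.0% |
| 5% | 0.95 | 10% | 5.9% |
| 10% | 0.90 | 21% | 9.0% |
| 15% | 0.85 | 32% | 14.8% |
| 20% | 0.80 | 44% | 23.8% |

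**Step 3: equal loss.** If both conditions lose the same fraction, the factor 1 − L appears in numerator and denominator and cancels. The ratio is unbiased even without a denominator.

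**Step 4: a part-completed period.** A period ended at 12 h and entered as a 24 h total gives that infant-period an apparent 50% reduction. The effect on the comparison depends on how many infants are affected. As an illustration, if 9 of 90 infants had this in the same condition, the mean log shift would be 0.10 × |ln 0.5| = 0.10 × 0.693 = 0.069, an apparent ratio of about 0.93.

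**The case against.** The strongest reply is that no bias is shown. The protocol gives no figure for lost monitoring and does not say that it varies by condition. The allowed breaks for cares and parent contact apply to all conditions. Equal loss cancels, and a 5% one-sided loss barely moves the error rate. All of this stands, so the point has to be conditional.

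A reader might infer that artefact and care time is cut out of the record. The text says only that such issues are identified. Reconciliation could equally serve to remove false events caused by poor contact, which would be proper handling, or to confirm events that needed intervention, which are part of the apnoea definition.

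A reader might also infer that keeping dropouts lowers the totals of the condition in which they deteriorated. The Analysis wording does not support this. It refers to infants who do not complete all treatments, and a wholly missing period adds no count. The protocol does not say that part-periods enter as full totals, and the visible text describes no withdrawal because of frequent events. Some pages were removed before review, so silence on withdrawal cannot be held against the plan.

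Finally, an offset, a link function or a minimum-valid-time rule may sit in an analysis plan that is not shown. That is fair for the model. It does not answer the point about data capture: the outcome is fixed in the protocol as a raw total, and the hours needed for a rate are not among the data to be recorded.

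**Conclusion.** The concern holds in a limited, conditional form. The event outcome is a raw total over a nominal 24 h, monitoring interruptions are expected, and nothing records valid time or relates the count to it. If loss is unequal between conditions, the condition with less valid time shows fewer events without any true effect. An assumed one-sided loss of 10% to 15% raises the false-positive rate from 5% to between 9.0% and 14.8%; at 5% or less the effect is small.

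These figures rest on the variance implied by n_c = 87, on Δ being |ln 0.60|, on a normal approximation for one pairwise comparison at N = 90, and on similar event rates in lost and valid time. Only one of the two primary outcomes is affected in this way.

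A reader might go further and infer that event-free days will be analysed as the log of the count plus a constant, which would shrink the 40% target. The protocol does not support that. Its statement "The observed baseline data was right-skewed, thus a log transformation was applied" concerns the pilot data used for sizing. The analysis is described only as a mixed effect model, and no added constant is mentioned.

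**What to change.** In Data Collection, add one field: valid monitored hours for each infant and condition period, read from the trace review already planned. State what happens to a flagged segment, and treat its events and its time alike, so that both are kept or both are left out.

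Analyse events as a rate within the planned mixed model, for example a count model with an infant random effect, condition and period as fixed effects, and the log of valid hours as offset. Enter any part-completed period with its own hours.

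The cost is one extra data field and a few sentences of wording. The rate assumes that events are about as frequent in lost as in valid time. If time is lost mainly around feeds, when the protocol expects more events, the offset corrects only part of the bias. Reporting valid hours by condition would let readers judge this.
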